8.1. Adverse Events Analyses

Adverse events analyses including the analysis of adverse events (AEs), Serious (SAEs) and other significant AEs will be based on GSK Core Data Standards. The details of the planned displays are provided in [Appendix 13: List of Data Displays](#).

8.2. Clinical Laboratory Analyses

Laboratory evaluations including the analyses of Chemistry laboratory tests, Haematology laboratory tests, Urinalysis, and liver function tests will be based on GSK Core Data Standards. The details of the planned displays are in [Appendix 13: List of Data Displays](#).

8.3. Other Safety Analyses

The analyses of non-laboratory safety test results including ECGs and vital signs will be based on GSK Core Data Standards, unless otherwise specified. The details of the planned displays are presented in [Appendix 13: List of Data Displays](#).

ECG Values of Potential Clinical Interest are defined as a QTc of > 450ms or a change from baseline in QTc of > 30ms per IDSL standard.

8.4. Planned Safety Analysis

[Table 5](#) provides an overview of the planned analyses, with further details of data displays being presented in [Appendix 13: List of Data Displays](#).

Table 5 Overview of Planned Safety Analyses

Endpoint	Absolute				Change from Baseline				Max Post BL			
	Summary		Individual		Summary		Individual		Summary		Individual	
	T	F	F	L	T	F	F	L	T	F	F	L
Exposure												
Extent of Exposure ^[1]	Y			Y ^[2]								
adherence to Q4W dosing ^[1]	Y			L								
Injection Needle												
Length and Gauge	Y			Y								
Adverse Events^[3]												
All AEs by SOC	Y											
All AEs by SOC and Toxicity ^[3]	Y			Y ^[4]								
Common AEs by freq ^[5]	Y	Y ^[6]										
Common Grade 2-5 AEs ^[5] by freq	Y											
All Drug-Related AEs by SOC and toxicity ^[3]	Y											
Common Drug-related Grade 2-5 AEs ^[5]	Y											
Serious and other significant adverse events												
All SAEs by SOC	Y											
Reason for Considering as a Serious Adverse Event (FDA)				Y								
All Drug-Related SAEs by SOC	Y											
Fatal SAEs				Y								
Non-Fatal SAEs	Y			Y								
Drug-related non-fatal SAEs	Y											
Withdrawal AEs	Y			Y								
Common Non-Serious AEs (FDA AAA)	Y											
Number of occurrences of Common Non-serious AEs by SOC (EudraCT)	Y											
Number of occurrences of SAEs, Drug-related	Y											

Endpoint	Absolute				Change from Baseline				Max Post BL			
	Summary		Individual		Summary		Individual		Summary		Individual	
	T	F	F	L	T	F	F	L	T	F	F	L
AEs, Fatal SAEs, and Drug-related SAEs (EudraCT)												
Cumulative AEs by visit	Y											
AEs by SOC and baseline 3 rd agent	Y											
Suicidality assessment												
PSRAE				Y ^[7]								
Columbia suicidality (C-SSR)	Y			^[18]								
Injection Site Reaction Adverse Events ^[14]												
ISR AEs (Event-Level) ^[20]	Y											
ISR AEs (Subject-Level) ^[21]	Y	Y										
ISR AEs (Subject-Level) by Visit and Severity ^[22]	Y	Y										
Maximum grade of ISR AEs (Subject-Level) by Needle Length ^[23]	Y											
Laboratory: Chemistry and Haematology												
Clinical Chemistry					Y							
%Lipids ^[24]					Y							
NCEP shifts in lipids		Y							Y			
Haematology					Y				Y			
Clinical Chemistry & Renal Biomarkers ^[13]					Y				Y			
Laboratory: Urinalysis (regardless of fasting status)												
Urine Dipstick	Y ^[9]			Y ^[8]								
Urine Concentration & Renal biomarkers ^[13]					Y							
Laboratory: Hepatobiliary												
Liver Assessment				Y ^[16]								
Hepatobiliary Abnormality criteria	Y ^[17]			Y								
Liver Chemistries				Y					Y ^[10]			
Laboratory: Markers												
Cardiovascular markers					Y ^[12]							

Endpoint	Absolute				Change from Baseline				Max Post BL			
	Summary		Individual		Summary		Individual		Summary		Individual	
	T	F	F	L	T	F	F	L	T	F	F	L
Bone markers					Y ^[11]							
ECG												
ECG findings	Y			Y								
ECG values					Y							
QTC	Y				Y				Y			
Other												
Vital Signs					Y							
Abacavir HSR				Y ^[15]								
Subjects who became Pregnant				Y								
Patient Profiles				[19]								
Skin Rash				Y								

NOTES :

- T = Table, F = Figures, L = Listings, Y = Yes display generated.
 - Stats Analysis = Represents TFL related to any formal statistical analyses (i.e. modelling) conducted.
 - Summary = Represents TFL related to any summaries (i.e. descriptive statistics) of the observed raw data.
 - Individual = Represents FL related to any displays of individual subject observed raw data.
1. Refer to Section 13.6.2 for defining Extent of Exposure and adherence, refer to Section 13.1.1 for defining compliance
 2. Includes reason for any dose change/interruption.
 3. For AEs reported more than once by a subject, the most severe intensity will be included.
 4. One listing of all AEs including verbatim text and preferred term, one showing the relationship between verbatim text, preferred term and SOC and another giving subject numbers for individual all treatment emergent AEs.
 5. Common AEs are those with ≥5% incidence in either treatment group summarised by frequency.
 6. Plots of incidence rates and relative risk with 95% CI for Q4W IM vs. Current ART.
 7. Four PSRAE listings: Event and Description (Section 1 - Section 2), Possible Cause (Section 3), Section 4 and Section 5 - Section 8.
 8. Listings for subjects with laboratory abnormalities for potential clinical concern, defined as any Grade1-4 toxicity, based on the DAIDs version described in Section 13.6.3 .
 9. Shift table summarising baseline vs. maximum post-baseline result for urine dipstick protein.
 10. Scatter plot of baseline vs. maximum post-baseline for ALT. Scatter plot of maximum ALT vs. maximum Bilirubin. Matrix plot of maximum liver chemistries.
 11. Bone biomarkers including: Bone-specific alkaline phosphatase, procollagen type 1 N-propeptide, type 1 collagen cross-linked C-telopeptide, osteocalcin, 25 hydroxy-Vitamin D.
 12. Cardiovascular biomarker : Glucose et al will be included in the summary of clinical chemistry, so there will be no separate summary for CV biomarkers
 13. Renal biomarkers: Urine Retinol Binding Protein, Retinol Binding Protein Cystatin C. CKD-EP1 GFR using Cystatin C (derived in Section 13.6.3) will also be summarized
 14. Repeat for CAB/RPV, CAB, RPV respectively.
 15. Separate listings for exposure to abacavir, history of drug allergies, family conditions, skin rash, symptoms, vital signs, individual symptoms and diagnostic category assignment.
 16. Separate listings for time of event: RUCAM score, biopsy, imaging, past/ current conditions and follow up
 17. One summary of subjects and another table showing Subject Ids.
 18. No lists are planned for eCSSR data.
 19. Patient profiles are not planned. But it can be produced in adhoc way, as necessary.
 20. Event-level summary: Percentages based on total number of ISR events within each treatment group including distribution of grade, duration, and event characteristics;

21. Subject-Level summary of characteristics of ISR AE (Overall and by Common ISRs); Percentage based on number of subjects within each treatment group; Includes distribution of grade and max grade, event characteristics, number of events per subject, rate of number of events per injection visit;
22. A corresponding plot of all grades and a separate plot of grade 3-5 events will be produced
23. Needle Length will be categorized into: <2 and ≥ 2 inch (please refer to Section 5.4 for the additional subgroup of ISR).
24. Please refer to Section 13.6.3 for defining percentage change from Baseline in Lipids

For the summary of Injection Site Reaction Adverse Events by Visit and Maximum Severity (Overall and by Common ISRs): ISRs will be assigned based on onset date to the most recent planned IM injection visit prior or equal to the AE onset date.

Maximum grade at each visit will be derived as the maximum grade among ISRs assigned to the particular visit, with consideration for whether the summary applies to a particular preferred term (vs. across preferred terms), drug-related associated to CAB and/or RPV, or stratification by subgroup (such as needle length).

Drug-related ISRs (based on investigator discretion) will be attributed to the causal agent (CAB vs. RPV) when this can be determined specifically based on the side of injection administration and the side of the reported ISR (as collected in the eCRF). If we are unable to determine the causal agent in those cases where both drugs are given on one side and the ISR is reported non-specifically, then the attribution to a specific causal agent will remain unknown.

Common ISR are defined as below:

Common ISR includes injection site pain, injection site induration, injection site nodules and any other ISR with $\geq 5\%$ subjects (for Q4W arm only). The same set of common terms will be applied to 'overall' (CAB and/or RPV), CAB alone, RPV alone.

ISRs will be attributed to the needle length (<2 , ≥ 2 inch) specifically based on the side of injection administration and the side of the reported ISR (as collected in the eCRF). If we are unable to determine the needle length in those events where both drugs are given on one side and their needle length are different, then the attribution to a needle length will remain unknown.

8.4.1. Planned safety statistical analysis

Statistical Analyses
Endpoints

 Change from baseline in bone markers at week 48
Covariates

 Treatment (Q4W IM, Current ART) Stratified randomisation strata (sex at Birth, Baseline ART third agent class), age, and additional subgroup for bone marker (TDF at baseline, body mass index category, and smoking status). Please see details for defining these subgroups/covariates in Section 5.4.2
Data Handling

 All data remains as is (observed).
Model Specification

 Bone marker results will be log-transformed. The change in the log-transformed data at week 48 from baseline (i.e. log of ratio of post-baseline value over baseline value) for each bone marker will be analysed for the comparison between the two treatment arms. An analysis of covariance (ANCOVA) model will be used with the above covariates. Age and Log-transformed biomarker at baseline will be included as continuous variables in the model and all other covariates will be included as categorical variables. Interaction between treatment and ART third agent class and interaction between treatment and TDF at baseline will be examined, as described in the modelling steps below.
Model Results Presentation

 The estimated coefficients of the ANCOVA model will be transformed back (exponential transform) to reflect the change in the ratio of post-baseline value over baseline value rather than the change in the log ratio. The change in the ratio can then be translated into percent change from baseline (e.g. the ratio $bb_{48}/bb_{bas} = 1.3$ can be translated into 30% increase from baseline). For each treatment, adjusted means of ratio and corresponding confidence intervals will be presented. The adjusted difference of the ratio (post-baseline value)/(baseline value) between the two treatments with the corresponding confidence interval and p-value will be presented. Modelling steps: 
 run separate statistical model with each interaction term at a time, i.e. each model including one interaction term and all covariates run a joint model including any significant terms from step 1 and all covariates If both interaction terms are included and significant in the joint model, the results will be presented by strata of third agent class X TDF at Baseline. If only one interaction term is significant in the Joint model, the statistical model will be rerun by excluding the nonsignificant interaction term (if any). The results will be presented by strata of the one significant interaction factor (third agent class or TDF at Baseline). If neither interaction term is significant, the statistical model will be rerun by excluding both interaction terms. The results will be presented for overall

Statistical Analyses
comparison between two arms.
Note: Interaction term between treatment and third agent class and/or TDF at baseline is considered to be 'significant' at the level of <10%.

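### SAP 8.4.1 reports the adjusted overall arm comparison for a bone marker only if neither 10% interaction test is significant, so about 16 to 20% of markers would lose it by chance

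*SAP*

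**What the plan says.** Section 2.2 lists renal and bone biomarkers, CAB LA + RPV LA against continued ART, among the exploratory objectives. Section 8.4.1 analyses the week 48 change in each log-transformed bone marker by ANCOVA, for the comparison between the arms. It then gives modelling steps for two interactions: "Interaction between treatment and ART third agent class and interaction between treatment and TDF at baseline will be examined".

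- Step 1: "run separate statistical model with each interaction term at a time".
- Step 2: "run a joint model including any significant terms from step 1 and all covariates".
- If both terms are significant in the joint model, "the results will be presented by strata of third agent class X TDF at Baseline".
- If only one is, the other is dropped and "The results will be presented by strata of the one significant interaction factor (third agent class or TDF at Baseline").
- In the remaining case, with no significant interaction, both terms are dropped, and only then are results presented for the overall comparison.

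An interaction "is considered to be 'significant' at the level of <10" per cent. The adjusted difference is to carry a confidence interval and p-value, but no level is given for it. In Section 13.13.7, Tables 3.77 and 3.78 summarise the bone markers descriptively, and Table 3.79 is the only model-based display.

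**The concern.** The stated aim is a comparison of two randomised arms, but the steps withhold that comparison whenever a pre-test is significant. No sentence keeps the overall contrast alongside the strata. A reader of Table 3.79 could then find some markers reported overall, some by two TDF levels, some by three classes and some by six cells, with the choice driven partly by noise. The stratum contrasts are less precise, and they are shown exactly when the data have been selected for looking different between strata. That invites statements about bone effects in subgroups.

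The SAP is more careful elsewhere. In Section 7.1.5.1 heterogeneity is also tested at 10%, but the overall primary estimate is always reported and level-specific results are added if needed. In Section 10.6 the treatment-by-baseline-score interaction is kept out of the model and footnoted.

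**Working it through.** The SAP gives no error rate for this procedure, so there is no plan figure to reproduce.

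**Inputs from the SAP.** Interaction level 10% and two interaction terms (8.4.1); third agent class with 3 levels and TDF with 2 (5.4.2); 570 randomised 1:1, INI capped at about 40% (2.3); five bone markers (8.4, notes to Table 5).

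**Assumed.** Treatment p-values read at two-sided 5%; the class mix; TDF prevalence and its relation to class.

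**Step 1: chance of losing the overall contrast.** For two independent tests at 10% with no true interaction: 1 − 0.90² = 1 − 0.81 = 19%.

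**Step 2: simulation of the full steps.** 6,000 trials per scenario, no treatment effect in any stratum. The ANCOVA contained sex, age, baseline value, BMI category, smoking, class and TDF. Each interaction was F-tested at 10%, the joint model was fitted if both were significant, and the prescribed contrasts were then tested. Monte Carlo standard errors are about 0.5 percentage points: √(0.19 × 0.81 / 6000) = 0.005.

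| N; PI/INI/NNRTI %; TDF use | Overall contrast lost | Any displayed p<0.05 | Overall model alone, p<0.05 | Any stratum p<0.05, given lost |
|---|---|---|---|---|
| 570; 20/35/45; 50% | 19.6% | 16.0% | 5.0% | 62% |
| 500; 17/33/50; 50% | 18.2% | 15.8% | 5.3% | 63% |
| 570; 20/40/40; 20% | 19.5% | 16.3% | 4.7% | 64% |
| 570; 33/33/34; 50% | 19.7% | 16.2% | 5.2% | 61% |
| 570; 20/35/45; 40/20/80% by class | 16.4% | 13.4% | 4.5% | 60% |

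In the first row the 15.95% splits into 3.82% from trials that kept the overall contrast and 12.13% from trials that went to strata. The case where both terms pass step 1 but neither survives the joint model restores the overall contrast. It occurs in about 1% of trials at most and is included in the figures.

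**Step 3: multiplicity or selection?** Without a pre-test, two independent contrasts at 5% give 1 − 0.95² = 9.75% and three give 1 − 0.95³ = 14.3%. Once the pre-test has sent results to strata, the chance is 60 to 64%. So selection matters as well as the number of contrasts.

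**Step 4: precision.** A stratum holding a fraction f of participants has a standard error of roughly 1/√f times the overall one: 1.41 at f = 0.5, 1.73 at f = 1/3, 2.24 at f = 0.2.

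**Step 5: five markers.** The expected number losing the overall contrast is 5 × 0.164 = 0.8 to 5 × 0.197 = 1.0, whatever the correlation between markers. If they were independent, at least one would lose it with probability 1 − 0.81⁵ = 65%. All five are measured in the same participants, so that figure is only indicative.

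**The case against.** The best defence has four parts.

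- **The analysis is exploratory and the rule is prespecified.** Both are true. Bone markers carry no success criterion, and the steps leave the analyst no discretion. But fixing the algorithm does not fix the contrast, and the result is still a formal model with intervals and p-values.
- **An interaction with TDF is plausible.** A TDF user who switches also stops TDF; a non-user does not. An overall average then depends on the enrolled TDF mix, and stratum results are informative. This stands, and the simulation covers only the no-effect case. It supports showing strata in addition to the overall comparison, not in its place.
- **The overall picture is not lost.** Tables 3.77 and 3.78 are unconditional and cover both arms, and nothing forbids adding the overall row to Table 3.79. This also stands. What the steps put at risk is the adjusted overall estimate with its interval and p-value.
- **The false-positive comparison sets unlike quantities side by side.** The 13 to 16% counts any of one to six contrasts, the 5% counts one, and Section 8.4.1 never says p-values are read at 5%.

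A reader might infer that the plan triples its false-positive rate for bone markers. The document does not support that as a flat statement: it needs the 5% reading and the any-contrast definition, and the 10% in 8.4.1 applies only to the interactions.

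**Conclusion.** The concern holds as a defect of reporting in an exploratory analysis. That the overall contrast is omitted conditionally follows from the text of 8.4.1 and needs no assumption.

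Its size under no true effect or interaction is about 16 to 20% of markers losing the adjusted overall contrast in Table 3.79. The lower end applies when TDF use depends strongly on third agent class. With p-values read at two-sided 5% and any displayed contrast counted, at least one false positive appears for about 13 to 16% of markers, against 5% for the single overall contrast. Class and TDF mixes are assumptions throughout.

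It would go too far to infer that trial conclusions are at risk: the primary and key secondary comparisons in Section 5.5 do not use this procedure. The change is worth making because it is specific and nearly free, and it makes the table answer the stated objective for every marker.

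**What to change.** In the modelling steps of Section 8.4.1:

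1. Name the treatment contrast from the main-effects ANCOVA (treatment plus the listed covariates, no interaction term) as the comparison for every bone marker, and always report it in Table 3.79 with its confidence interval and p-value.
2. Report both interaction p-values beside it.
3. Where an interaction is below 10%, add by-stratum estimates with confidence intervals, labelled exploratory and unadjusted for multiplicity and pre-test selection.

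This keeps the named contrast at its nominal level (4.5 to 5.3% in the simulations), and no marker loses it. It does not remove the multiplicity of the supplementary stratum intervals, which are still selected by the pre-test; the label is there to say so. The cost is a change of SAP wording and one extra row or block in an existing table.

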9. PHARMACOKINETIC ANALYSES

The GSK Division of Clinical Pharmacology Modelling and Simulation (CPMS) will be responsible for the PK analysis of CAB. The Division of Global Clinical Pharmacology at Janssen Research and Development will be responsible for conduct or oversight of the PK analysis for RPV.

All PK and PK/PD displays will be based on the PK Population.

9.1. Primary Pharmacokinetic Analyses

9.1.1. Endpoint / Variables

A population-based PK analysis will be described under separate Population-PK Reporting and Analysis Plans. for CAB LA and RPV LA.

Table 6 provides an overview of the planned analyses based on CAB/RPV concentration data only with full details being presented in Section 13.13: List of Data Displays.

Table 6 Overview of Planned Pharmacokinetic Analyses

	Stats Analysis			Summary		Individual	
	T	F	L	T	F	F	L
Pharmacokinetic [5]							
Plasma CAB concentration by Visit				Y ^[1] [2]	Y ^[1] [3][4]	Y ^[3]	Y
Plasma RPV concentration by Visit				Y ^[1] [2]	Y ^[1] [3][4]	Y ^[3]	Y
Steady state concentration				Y ^[1]			
Pharmacokinetic/Pharmacodynamic							
CAB/RPV last trough and Week-8 concentration by Snapshot virologic Response				Y			
Analysis of Snapshot 'HIV-1 RNA \geq 50' at Week 48 by last trough CAB/RPV concentration, Week 8 trough concentration, and subgroup[6] – Univariate analysis /multivariate analysis	Y						
Individual CAB/RPV Concentration-Time Profiles for Subjects with HIV-1 RNA \geq 50c/mL at Week 48					Y		

	Stats Analysis			Summary		Individual	
	T	F	L	T	F	F	L
Last trough CAB/ RPV concentration and Week-8 trough concentration by snapshot 'HIV-1 RNA≥50' at Week 48					Y		
Change from baseline in 2hr post-dose QTc and 2hr post-dose CAB & RPV concentration at Week 4B, Week 48;						Y	
Maximum Change from Baseline(CFB) in ALT/Total Bilirubin versus Last Trough CAB/RPV Concentrations						Y	
Maximum Toxicity Grades of Most Frequently Reported AEs versus Last Trough CAB/RPV Concentrations						Y	

NOTES:

- T = Table, F = Figure, L = Listings, Y = Display generated.
 - Stats Analysis = Represents TFL related to any formal statistical analyses (i.e. modelling) conducted.
 - Summary = Represents TFL related to any summaries (i.e. descriptive statistics) of the observed raw data.
 - Individual = Represents FL related to any displays of individual subject observed raw data.
1. For both 'all' concentration and the 'evaluable' concentration. The evaluable concentration is derived from samples collected within pre-specified Time window (Section 13.6.5)
 2. For both 'untransformed' and 'log –transformed' statistics.
 3. The plots will be produced for the untransformed scale (i.e., a linear plot) and the log transformed scale (i.e., log-linear plot), separately.
 4. Separate plots will be produced for Mean (SD) and Median concentration.
 5. Standard summary statistics for concentration data will be calculated (i.e., mean, standard deviation, median, minimum and maximum). For Logarithmically transformed data, the summary statistics (i.e. geometric mean, coefficient of variation on geometric mean, 95% confidence interval for the geometric mean and standard deviation) will also be calculated.
 6. Please refer to Section 5.4. i.e. randomisation strata, baseline and demographic factors, and additional subgroup for PK analysis

9.1.2. Planned Pharmacokinetic statistical analysis

Planned PK statistical analysis
Steady state concentration
Endpoints

 • log_e-transformation of the Trough/Pre-dose plasma concentrations (CAB/RPV) on Week 16-48
Covariates

 • Study Week
Data Handling

 • All data remains as is (observed).
Model Specification

 • A mixed effects ANOVA model will be fitted with Week (continuous variable) as a fixed effect and subject as a random effect for each analysis separately. The Kenward & Roger (KR) degrees of freedom approach will be used. The coefficient for the slope of the day effect on the log_e-scale will be used to evaluate steady state for each drug (CAB/RPV). The 90% confidence intervals for the slope for each treatment will be calculated. If it does not appear that steady-state has been demonstrated, early weeks (e.g. Week 16, 20, 24, etc...) results will be dropped

Planned PK statistical analysis
and the analysis repeated.
Model Checking & Diagnostics

 The Steady state will be claimed (the coefficient for the slope of the Week effect on the (natural) log scale was close to 0 or the 90% CI for the slope estimate included zero. If steady-state is not demonstrated, concentrations from early weeks (e.g. Week 16, 20, 24, etc...) dropped in sequence and the analysis repeated until either steady state shown or only two timepoints remain.
Model Results Presentation

 The coefficient for the slope of the day effect on the \log_e-scale, its Standard error and 90% interval will be presented.
Population PK Analysis
A population-based PK analysis will be done under separate Population-PK Reporting and Analysis Plans.
Exposure - antiviral activity analysis
Endpoints
Snapshot 'HIV-1 RNA \geq 50' at Week 48
Covariates
Randomisation strata (sex at Birth and baseline ART third agent class), demographic and Baseline characteristics (age <50 vs \geq 50, race, baseline CD4, baseline viral load, and baseline CDC subgroups), and additional subgroup/covariates for PK/PD efficacy analysis (last CAB/RPV trough concentration, CAB/RPV trough concentration at nominal visit of Week 8, Baseline BMI, length of injection needle). Please see details for defining these subgroups/covariates in Section 5.4.2.
Data Handling

 All data remains as is (observed).
Model Specification
Logistic regression will be used to exam the correlation between the endpoint (Snapshot 'HIV-1 RNA \geq 50') at Week 48 and the covariates/subgroups. CAB/RPV trough concentration will be included in the models as continuous variables. This logistic regression analysis will be performed for each covariate, separately (univariate analysis), and will also be performed with one multivariate analysis using Backward stepwise selecting approach to identify the covariates potentially affecting virologic response.
Model Checking & Diagnostics
For the multivariate analysis, a logistic regression model that best predicts the dependent variable (i.e. 'HIV-1 RNA \geq 50') from the independent variables (i.e. covariates/factors with $P < 0.15$ from univariate analysis) will be determined using the backward stepwise selecting approach. The last trough and Week-8 trough PK concentrations will be logarithmically transformed with base of 2. The analysis will start with all covariates in the model and remove a covariate with the largest p-value (i.e. the least statistically significant) each time and continue until the stopping rule is reached

Planned PK statistical analysis
when all remaining covariates have p-value <15%.
Model Results Presentation

 The odds ratio, 95% confidence interval, and P value will be presented. Estimated effect represents the change in log odds for a two-unit increase in the pk concentration

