Design Features	
 Phase III, randomized, open-label, active-controlled, multicenter, parallel-group, non-inferiority study designed to assess the antiviral activity and safety of a two-drug regimen of CAB LA + RPV LA compared with maintenance of current ART The ATLAS study comprises a Screening Phase (up to 35 days), a Maintenance Phase (Day 1 to Week 52), and the randomized portion of the study will continue with an Extension Phase up to at least 96 weeks. Additionally, any participant who receives at least a single dose of CAB LA and/or RPV LA and discontinues the CAB LA + RPV LA regimen will enter the Long-term Follow-up Phase and will initiate highly active antiretroviral therapy (HAART) for at least 52 weeks after the last dose of CAB LA and/or RPV LA
Dosing	
 Maintenance Phase: 1:1 randomization to continue current ART or be switched to the CAB LA + RPV LA regimen through 52 weeks Extension Phase: CAB LA + RPV LA
Treatment Assignment	
 N =570 randomized at start of Maintenance Phase At Week 52, participants randomized to continue on current ART will have the option to either continue study participation by switching to CAB LA + RPV LA in the Extension Phase, or to complete their study participation at

Overview of Study Design and Key Features	
	Week 52. 
 • GSK RandAll NG used to generate randomization schedules • Stratified Randomization by baseline third agent class (PI, INI, or NNRTI) and sex at birth.
Interim Analysis	
 • 50% of subjects completing Week 24 • Continuous time monitoring of confirmed virologic failure (CVF) (both in the NNRTI strata and overall) • The main analysis will be conducted to evaluate the primary objective of the protocol at Week 48. • Further data cuts and analyses may be conducted as necessary in order to support regulatory submissions and publications.

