13.3.5. Assessment Window for PK concentration Data

For PK concentration data at the withdrawal/unscheduled/LTFU Month1 visits during Maintenance or Extension phase, the visit will be slotting to the analysis visit per the following steps:

- Identify the ‘last nominal visit’ with the PK pre-dose assessment performed prior to the visit to be slotted during the same study phase
- The unscheduled/withdrawal/LTFU Month1 visit will be slotted to the nominal visit corresponding to the earliest of the next planned injection visit or next planned PK assessment visit (excluding timepoints with storage PK collection), that is subsequent to the ‘last nominal visit’ during the same study phase.

During Maintenance or Extension phase, the planned nominal visits for PK Pre-dose are Week 4b, 8, 12, 16, 20, 24, 28, 32, 36, 40, 44, 48, 52, 96 for Q4W arm; and are Week 56b, 60 for Current ART arm.

For example, if a subject has the ‘last nominal visit’ (with PK pre-dose assessment) at Week 24 and then withdraws (around Week 28) with a PK assessment labelled at ‘LTFU month1’ post Week 24 during the Maintenance phase, this assessment will be slotted to the subsequent planned nominal visit of Week 28.

There will be no slotting for planned nominal visits (i.e. analysis visit =visit).

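### The steady-state rule takes a non-significant slope as proof of no slope and drops early weeks to reach it, so slow rises will usually, and moderate rises often, be declared at steady state

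*SAP*

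**What the plan says.** Section 9.1.2 of the SAP analyses log-transformed "Trough/Pre-dose plasma concentrations (CAB/RPV) on Week 16-48". The model is simple: "A mixed effects ANOVA model will be fitted with Week (continuous variable) as a fixed effect and subject as a random effect". It adds that "The 90% confidence intervals for the slope for each treatment will be calculated".

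The decision rule, under the model-checking heading of the same section, has two branches joined by *or*. Steady state is claimed if "the coefficient for the slope of the Week effect on the (natural) log scale was close to 0", or if "the 90% CI for the slope estimate included zero". If neither holds, concentrations from early weeks are "dropped in sequence and the analysis repeated until either steady state shown or only two timepoints remain".

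No number is attached to the first branch. The section gives no equivalence range, no minimum time span beyond two timepoints, and no allowance for repeated looks. The results go to Tables 4.5 (all concentrations) and 4.6 (evaluable concentrations) in Section 13.13.11.

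**The concern.** A confidence interval that contains zero shows only that the data did not exclude a flat line. It may also contain slopes that matter. The rule therefore rewards imprecision: fewer samples, more variable assays or a shorter window all make steady state easier to claim.

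The dropping step makes this worse. If the full window gives clear evidence of a rise, the plan does not report that steady state was not shown. It shortens the window and tests again, with a wider interval each time. The rule is thus too strict at the first look, where a large sample flags negligible drift, and too lax at the last.

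At stake is the conclusion that Tables 4.5 and 4.6 exist to deliver. They could report steady state for troughs that are still accumulating.

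**Working it through.** The SAP states no error rate, power or bound for this rule, so there is no figure of its own to reproduce.

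**Inputs from the SAP**
- Visits: Section 13.3.5 says that "the planned nominal visits for PK Pre-dose are Week 4b, 8, 12, 16, 20, 24, 28, 32, 36, 40, 44, 48, 52, 96" for the Q4W arm. Weeks 16 to 48 therefore give 9 visits and up to 8 successive fits (9 visits down to 2).
- Size: "N =570 randomized at start of Maintenance Phase", 1:1, so about 285 on the injectable arm.
- Interval: 90% two-sided, z = 1.645.

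**Assumptions not in the SAP**
- n = 260, to allow for missing samples.
- Within-participant SD s of 0.3 or 0.5 on the log scale.
- Complete data and independent errors. A random-intercept model then gives the within-participant slope.
- Only the CI branch is applied. The close-to-zero branch can only add declarations, so the rates below are lower limits for the full rule.

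**1. Loss of precision.** Slope SE = s / √(n·S), where S is the sum of squared deviations of the visit weeks from their mean.

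| Visits left | S | SE relative to 9 visits |
|---|---|---|
| 9 (Weeks 16–48) | 960 | 1 |
| 7 | 448 | √(960/448) = 1.46 |
| 5 | 160 | √(960/160) = 2.45 |
| 2 (Weeks 44, 48) | 8 | √(960/8) = 10.95 |

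**2. What this does to the pass mark.** The interval includes zero when the observed slope is below 1.645 × SE. Expressed as a rise over 32 weeks at s = 0.3:
- Nine visits: 32 × 1.645 × 0.3/√(260 × 960) = 0.032 on the log scale, about 3%.
- Two visits: 32 × 1.645 × 0.3/√(260 × 8) = 0.346, about 41%.

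At s = 0.5 the same sums give 0.053 (about 5%) and 0.577 (about 78%).

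**3. Chance of a steady-state claim under a constant log-linear rise.** At the last look the probability is Φ(1.645 − d/SE) − Φ(−1.645 − d/SE), with d the log rise over 4 weeks and SE = s√(2/n). For a 25% rise at s = 0.3: d = ln(1.25)/8 = 0.0279, SE = 0.0263, d/SE = 1.06, giving 0.72. The last column was simulated (200,000 runs per row and SD). Cells show s = 0.3 / s = 0.5.

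| Rise, Weeks 16–48 | Full window only | Last look only | Whole sequence |
|---|---|---|---|
| 10% | 0.1% / 9% | 87% / 89% | 95% / 98% |
| 25% | 0% / 0% | 72% / 83% | 75% / 90% |
| 50% | 0% / 0% | 39% / 69% | 39% / 72% |

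Separate sets of 800 runs gave 72–76% / 90–91% for the 25% rise and 36–39% / 67–75% for the 50% rise. For an exponential approach to plateau from Week 4 with a 15-week half-life (87% of plateau at Week 48), the sequence declares steady state in about 65–69% / 87%.

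**4. The opposite error at the first look.** For a 3% total drift the slope is ln(1.03)/32 = 0.00092 per week.
- s = 0.3: SE = 0.00060, ratio 1.54; the interval excludes zero in about 46% of trials.
- s = 0.5: SE = 0.00100, ratio 0.92; about 24%.

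Allowing for simulation error, that is about 20 to 50%.

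**The case against.** **The stronger reading fails.** A reader might infer that the procedure ends in steady state whatever the truth, or that any rising trough will usually be passed. The SAP does not support that. It stops at two timepoints, so steady state can remain undeclared. It gives neither a within-participant SD nor an expected slope. For steep rises the rule often does refuse: with 240 to 285 participants, a rise of 2% per week (about 90% over Weeks 16 to 48) is declared in 0% of runs at SD 0.20, 13–20% at 0.35 and 43–49% at 0.50.

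**Dropping weeks has a purpose.** It looks for the point at which accumulation levels off. With half-lives of 4 to 8 weeks to plateau, the median retained start week falls at about 94–97% of plateau, which is reasonable. A log-linear rise with no plateau is the least favourable case. This defence weakens at a 15-week half-life, as shown above.

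**An equivalence range is not stricter everywhere.** A range of 0.80–1.25 applied to Weeks 24–48 accepts the 10% rise in 99–100% of runs. It accepts the 25% rise, which is 1.25^(24/32) = 1.18-fold over that window, in about 84% at SD 0.3 and 46–48% at SD 0.5. It is clearly stricter for the 50% rise (0%). So the range must be chosen for the drift that matters. This limits the fix and does not rescue the rule.

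**Reach is small.** The slope, its standard error and the 90% interval are reported. Troughs are also summarised by visit (Tables 4.1–4.4) and plotted. Steady state is not named as an objective or endpoint in Section 2.2. The exposure–response models use the last and Week 8 troughs regardless of this result. All of this stands and bounds the consequence.

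**Conclusion.** The point holds in a bounded form. The rule as stated is unsound, not merely under-described: it equates non-significance with no slope, and its own repeat step turns clear evidence of a rise into a claim of steady state by discarding information. Slow rises will usually, and moderate rises often, be declared at steady state.

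The percentages depend on the assumed SD, sample size and shape of the curve, none of which the SAP fixes apart from the number randomised. The 11-fold loss of precision does not depend on SD or sample size; it follows from the visit schedule, given complete data and constant SD. The missing bound on the close-to-zero branch is plain from the text.

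The consequence is a possibly misleading conclusion in Tables 4.5 and 4.6. It does not reach the primary endpoint. The change should be made, but it is not critical to the trial.

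**What to change.** - Keep the mixed model and the 90% interval, which suits an equivalence test at 5% on each side.
- Fix the assessment window in advance: start week and minimum span.
- Declare steady state only if the 90% CI for the model-based fold change in trough over that window lies wholly inside a pre-stated range that the sponsor justifies. A range of 0.80–1.25 is one example; a tighter one is needed if a 10–25% rise is to be excluded.
- Delete the close-to-zero criterion.
- If start weeks are still to be searched to find when the plateau is reached, apply the same equivalence criterion at each step, with a fixed minimum span, in place of the interval-includes-zero rule.
- In Tables 4.5 and 4.6, report the weeks retained and the fold change with its CI.

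The cost is a few lines of SAP text and a little extra output. The downside is that steady state may not be declared when drift is moderate or samples are sparse. In those cases the tables should say that it was not shown.
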